7 STUDY ASSESSMENTS AND PROCEDURES

Study assessments and procedures are described in the SoA ([Section 8.1](#)).

The Investigator and Sponsor will conduct the study in accordance with ICH Good Clinical Practice (GCP) and local regulations. Adherence to the study design requirements, including those specified in the SoA, is essential and required for study conduct, and the Investigator must ensure that study procedures are performed as described in the protocol. During the study, procedures and observations will be monitored to confirm that study requirements are being followed as outlined in the SoA.

7.1 Informed Consent Form

Informed consent may be obtained any time prior to screening procedures, no visit window applies. ICFs for enrolled patients and for patients who are not subsequently enrolled will be maintained at the study site.

The anticipated consents to be used in the study are listed below; however, individual Institutional Review Boards (IRBs)/Ethics Committees (ECs) may require additional consent.

1. General Informed Consent: Consents patients for all required study procedures.
2. Optional Tissue Study Informed Consent (US patients only): Consented patients who are able and willing to provide fresh tumor tissue at C2D1, and EOT. As noted in the eligibility criteria, a fresh biopsy at screening is also preferred if safe and feasible to obtain and consented to by the patient.

7.2 Screening

All screening procedures must be performed within 28 days prior to the first treatment (Cycle 1 Day 1), unless otherwise stated in the SoA ([Section 8.1](#)). Procedures conducted as part of the patient's routine clinical management (e.g., blood count) and obtained before signing the ICF may be used for screening or baseline purposes provided the procedures meet the protocol-specified criteria and were performed within the time frame defined in the SoA.

All inclusion and exclusion criteria will be reviewed by the Investigator or qualified designee to ensure that the patient qualifies for the study. Eligibility will also be reviewed by the Sponsor or designee. In the event of borderline laboratory results or other factors that are deemed clinically insignificant, procedures may be repeated to meet eligibility requirements fully and/or discussed with the Medical Monitor for potential inclusion.

Demographic data, baseline characteristics, and medical and surgical history will be obtained during screening.

History of the cancer under study will be recorded separately. This will include, but is not limited to, data on histopathological diagnosis, grading, staging, sites of metastases, prior treatments, prior best response, and diagnostic and biomarker data.

7.3 Screen Failures

Screen failures are defined as patients who consent to participate in the clinical study but are not subsequently assigned to study treatment. A minimal set of screen failure information is required to ensure transparent reporting of screen failure patients to meet the Consolidated Standards of Reporting Trials publishing requirements and to respond to queries from regulatory authorities. Minimal information includes demography, screen failure details, eligibility criteria not met, and any SAEs related to study procedures that occur after the ICF was signed.

Individuals who do not meet the criteria for participation in the study may rescreen by repeating the individual assessment(s) for which they failed.

7.4 Prior, Concomitant, and Post-Treatment Medication Reviews

Prior medications: Prior medications taken by the patient within 30 days of enrollment into the study and all ongoing medications will be recorded. Prior treatments for the current cancer will be recorded separately and not listed among prior medications.

Concomitant medications: Medications taken by the patient during the study will be recorded from the date of consent through the 30-day safety follow-up.

Concomitant cancer-related procedures: Cancer-related procedures during the study will be recorded from the date of consent through the 30-day safety follow-up.

Post-treatment anticancer therapy: The Investigator or qualified designee will review all new anticancer therapy initiated after the last dose of study treatment. If a patient initiates a new anticancer therapy within 4 weeks after the last dose of study treatment, the 30-day safety follow-up visit must occur before the first dose of the new therapy. Once new anticancer therapy has been initiated, patients will move into survival follow-up.

7.5 Treatment Period

Patients should continue to receive study treatments and assessments as defined in the SoA ([Section 8.1](#)) until treatment discontinuation criteria are met ([Section 6.1](#)).

7.6 End-of-Treatment Visits

EOT visit requirements are described in the SoA ([Section 8.1](#)).

The EOT visit should occur as soon as possible at the time both study treatments are discontinued. If the EOT visit occurs approximately 30 days from the last dose of study treatment, the procedures performed at the EOT visit can serve as the 30-day safety follow-up and do not need to be repeated.

7.6.1 30-Day Safety Follow-up

The 30-day safety follow-up visit is required for all patients 30 days (+7 days) after the last dose of study treatment or before initiation of new anticancer treatment, whichever comes first. Patients with an AE of Grade ≥ 2 will be further followed until the resolution of the AE

to Grade 0-1 or until initiation of new anticancer therapy, whichever occurs first. Patients with an ongoing treatment-related AE must be followed until it resolves, becomes stable, or is considered not clinically significant by the Investigator.

7.6.2 90-Day Safety Follow-up

All patients who discontinue pembrolizumab will be contacted (telephone communication or clinic visit, at the Investigator's discretion) for the follow-up of AEs 90 days (+7 days) after the last dose of pembrolizumab or before initiation of new anticancer treatment, whichever comes first.

7.6.3 Survival Follow-up

All patients who have discontinued the study treatment will continue to be followed for survival information, including survival status and initiation of new anticancer treatment(s). Survival information will be collected every 12 weeks (± 7 days) (telephone communication or in clinic visit) until the study ends. Survival data will be obtained from public records for patients who have been lost to follow-up.

Patients who discontinue study treatment for reasons other than PD will continue to have tumor assessments performed every 6 weeks until PD or the initiation of new anticancer therapy.

7.7 Imaging Assessments

For all patients, tumor response assessment will be obtained by radiographic imaging with contrast-enhanced CT (preferred) or MRI evaluation. Optimal anatomic coverage for most solid tumors include the chest, abdomen, and pelvis. Coverage should encompass all areas of known predilection for metastases in the disease under evaluation and should additionally investigate areas that may be involved based on signs and symptoms of individual patients. In general, lesions present at baseline should be followed using the same imaging methodology and imaging equipment at subsequent assessments.

Tumor response assessments will be based on evaluation of response of target, non-target, and new lesions according to RECIST v1.1, as detailed in [Appendix 5](#) (all measurements should be recorded in metric notation). Following initial objective response (PR or CR per RECIST v1.1), confirmatory imaging studies should be obtained 4 to 6 weeks later ([Eisenhauer et al 2009](#)).

Before stopping treatment, confirmation of PD should be considered by imaging no less than 4 weeks after initial progression.

The timing of on-study imaging should follow calendar days and **should not** be adjusted for delays in treatment administration or for visits. The same imaging technique should be used in a patient throughout the study for consistency.

For patients who discontinue study treatment for reasons other than PD, radiographic scans should continue according to the respective schedule of assessment until PD, initiation of new anticancer therapy, withdrawal of consent, or at least 15 months after the last patient is

randomized in the study, whichever comes first. Additional imaging may be performed if clinically indicated per the Investigator's discretion.

Brain MRI with or without contrast is the preferred brain imaging modality; however, CT is acceptable if MRI is clinically contraindicated. Patients with treated or untreated parenchymal brain metastases, leptomeningeal disease, or current active malignant epidural disease are excluded from participation in the study (see [Section 4.2](#)). Patients with previously treated epidural disease are allowed as long as disease is inactive. Patients are not required to have brain imaging at screening unless there are suggestive clinical symptoms/suspicion.

During the study, brain CT/MRI scans should be conducted if clinically indicated by development of new specific symptoms.

7.8 Safety Assessments

7.8.1 Physical Examination

The Investigator or qualified designee will perform a complete physical examination during the screening period, on Day 1 of each cycle, and at the end of the treatment period as specified in the SoA ([Section 8.1](#)). Clinically significant abnormal findings during screening should be captured in the medical history.

Patients on the danvatirsen and pembrolizumab arm will have a targeted physical examination as directed by disease, signs, and symptoms performed on Days 8 and 15 of each cycle and at the 30-day safety follow-up visit. New and clinically significant abnormal findings during the study should be recorded as AEs.

Patients on the pembrolizumab arm will have a targeted physical examination as directed by disease, signs, and symptoms performed on Days 8 and 15 of each cycle through cycle 4 and at the 30-day safety follow-up visit. New and clinically significant abnormal findings during the study should be recorded as AEs. Beginning with cycle 5, patients on the pembrolizumab arm are only required to have an in person visit on Days 8 and 15 if clinically indicated therefore the Investigator or qualified designee will contact the patient via a phone call on Days 8 and 15 to evaluate their general health status and monitor for new AEs and concomitant medications.

7.8.2 Clinical Laboratory Parameters

The hematology panel will consist of complete blood count (hemoglobin, hematocrit, erythrocytes [i.e., red blood cell count], and leukocytes [i.e., white blood cell count]) with differential (i.e., basophils, eosinophils, lymphocytes, monocytes, neutrophils) and platelet counts.

The clinical laboratory tests are listed in [Table 4](#); the timing and frequency of the laboratory tests are provided in the SoA ([Section 8.1](#)). These assessments should be performed at the local laboratory associated with the Investigator site.

Table 4: Clinical Laboratory Tests

Hematology	Chemistry	Coagulation	Urinalysis	Pregnancy Test	Other
Hemoglobin	ALT	INR			
Hematocrit	AST	aPTT or PTT			
WBC (with differential)	Alkaline phosphatase				
Neutrophils	Sodium				
Lymphocytes	Potassium				
Monocytes	Magnesium				
Eosinophils	Chloride				
Basophils	Total calcium				
RBC count	BUN or Urea				
Platelets	Creatinine				
	Glucose (non-fasted)				HIV viral load**
	Total bilirubin				
	Albumin				
	Phosphorous **(or phosphate)				
	LDH				
	Amylase**				
	Lipase**				
	Bicarbonate (or carbon dioxide)				
	Uric acid**				

* Morning, cortisol required at screening and when clinically indicated (adrenal insufficiency suspected). Blood sample should be drawn with ACTH.

** To be obtained only as clinically indicated for eligibility and throughout the study.

Abbreviations: ACTH = adrenocorticotrophic hormone; ALT = alanine aminotransferase; aPTT = activated partial thromboplastin time; AST = aspartate aminotransferase; BUN = blood urea nitrogen; HBV = hepatitis B virus; HCV = hepatitis C virus; HIV = human immunodeficiency virus; INR = international normalized ratio; LDH = lactate dehydrogenase; RBC=red blood cell; TSH = thyroid-stimulating hormone; WBC = white blood cell

7.8.3 Vital Signs, Height, and Weight

Vital signs include temperature, pulse, respiratory rate, blood pressure, and oxygen saturation. Weight should be assessed at the beginning of each cycle, per the SoA (Section 8.1). Height will be measured at screening only.

7.8.4 Electrocardiogram

A standard 12-lead ECG in triplicate will be performed using local standard procedures as specified in the SoA (Section 8.1). Three consecutive 12-lead ECGs (triplicates) will be performed approximately 2 minutes apart to determine mean QTc (average of triplicates). If

the mean QTc is prolonged (>500 msec), the ECGs should be re-evaluated by a qualified person at the institution for confirmation and should be repeated as clinically indicated. Additional triplicate ECGs may be performed as clinically indicated. Clinically significant findings seen on follow-up ECGs should be recorded as AEs.

7.8.5 ECOG Performance Status

ECOG performance status ([Appendix 1](#)) will be assessed as specified in the SoA (see [Section 8.1](#)).

7.9 Adverse Events

7.9.1 Definition of an Adverse Event

An AE is defined as any untoward medical occurrence in a patient administered a medicinal product that does not necessarily have a causal relationship with this treatment. An AE can, therefore, be any unfavorable and unintended sign (including an abnormal laboratory finding), symptom, or disease temporally associated with the use of a medicinal (investigational) product, whether or not related to the study (investigational) product. This includes an exacerbation of pre-existing conditions or events, concurrent illnesses, drug interactions, or the significant worsening of the indication under investigation. Anticipated fluctuations of pre-existing conditions, including the disease under study that does not represent a clinically significant exacerbation or worsening, need not be considered AEs.

Symptoms of the disease under study/lack of efficacy/cancer progression should not be classified as an AE if they are within the normal day-to-day fluctuation or expected progression of the disease.

It is the responsibility of the Investigator to document all AEs that occur during the study. AEs should be reported on the appropriate eCRF.

7.9.2 Definition of a Serious Adverse Event

An SAE is any untoward medical occurrence at any dose (including those occurring after the ICF is signed and before dosing) that:

- Results in death
- Is life-threatening (patient is at immediate risk of death from the event as it occurred)
- Requires inpatient hospitalization or prolongation of existing hospitalization
- Results in persistent or significant disability/incapacity
- Results in a congenital anomaly/birth defect
- Meets criteria for an important medical event, as described below

Important medical events that may not result in death, are not immediately life-threatening, or do not require hospitalization may be considered SAEs when, based on appropriate medical judgment, they may jeopardize the patient and may require medical or surgical intervention to prevent one of the outcomes listed in this definition. Examples of such events

include allergic bronchospasm requiring intensive treatment in an emergency room or at home, blood dyscrasias or convulsions that do not result in inpatient hospitalization, or the development of drug dependency or drug abuse.

For SAE reporting purposes, hospitalization is defined as inpatient hospital stay. Hospitalizations for elective surgery or other medical procedures that are not related to a treatment-emergent adverse event (TEAE) are not considered SAEs. Hospitalization that, in the opinion of the Investigator, is unrelated to the study treatment(s) and due to purely non-medical circumstances (e.g., respite care, lack of a caretaker at home, lack of transportation home) is also not considered to be an SAE.

Death should not be considered an SAE. The primary reason for a patient's death should be reported as the SAE, with death reported as the outcome.

7.9.3 Severity of Adverse Events

The severity of the AE will be graded according to the CTCAE v5.0. Only AEs not listed in the CTCAE should be graded as summarized in [Table 5](#).

Table 5: CTCAE AE Grading

CTCAE Grade	Equivalent To:	Definition
Grade 1	Mild	Discomfort noticed but no disruption of normal daily activity
Grade 2	Moderate	Discomfort sufficient to reduce or affect daily activity; no treatment or medical intervention is indicated, although this could improve the overall well-being or symptoms of the patient
Grade 3	Severe	Inability to work or perform normal daily activity; treatment or medical intervention is indicated to improve the overall well-being or symptoms; delaying the onset of treatment is not putting the survival of the patient at direct risk
Grade 4	Life-threatening/disabling	An immediate threat to life or leading to a permanent mental or physical condition that prevents work or performing normal daily activities; treatment or medical intervention is required to maintain survival
Grade 5	Death	AE resulting in death

Abbreviations: AE = adverse event; CTCAE = Common Terminology Criteria for Adverse Events

7.9.4 Relationship of Adverse Events to Study Treatment

For each AE/SAE, a causality assessment must be provided by the Investigator. The Investigator will use clinical judgment to determine whether or not an AE/SAE was related to each study treatment, as outlined below.

Related is defined as one of the following:

- **Definitely related:** This applies when, after careful medical consideration, there is almost no consideration of other causation.
- **Probably related:** There is a clinically plausible time sequence between onset of the AE and study treatment administration. The AE is unlikely to be caused by a concurrent or underlying illness, other drugs, or procedures. If applicable, the AE follows a clinically consistent resolution pattern upon withdrawal of study treatment.
- **Possibly related:** There is a clinically plausible time sequence between onset of the AE and study treatment administration, but the AE could also have been caused by the concurrent or underlying illness, other drugs, or procedures. Information regarding study treatment withdrawal may be lacking or unclear. “Possible” should be used when study treatment administration is one of several biologically plausible causes of the AE.

Not Related is defined as one of the following:

- **Unlikely related:** The AE is most likely due to a cause not related to study treatment administration. However, association with the study treatment cannot be completely ruled out.
- **Unrelated:** Another cause of the AE is most plausible, and a clinically plausible temporal sequence is inconsistent with the onset of the AE and study treatment administration and/or a causal relationship is considered biologically implausible.

For the purpose of regulatory reporting requirements, causal relationships of definite, probable, and possible will be considered treatment-related, while unlikely and unrelated will be considered not treatment-related.

7.9.5 Clinical Laboratory Adverse Events

A clinical laboratory AE is any laboratory value that is deemed clinically significant by the Investigator and is accompanied by one of the following:

- Requires a medical intervention
- Requires a modification or interruption of study treatment
- Is accompanied by clinical symptoms

Laboratory abnormalities that do not require medical intervention should not be recorded as AEs and will be captured and reported in the laboratory section of the clinical study report (CSR). If a medical intervention occurs, it should be recorded as a treatment with the abnormal laboratory finding as the AE (e.g., anemia with treatment required and blood transfusion recorded as a procedure, hyperglycemia with treatment required and change in insulin dose recorded on the concomitant medications eCRF).

The Investigator should decide, based upon the AE criteria and the clinical condition of the patient, whether a change in a laboratory parameter is clinically significant and therefore represents an AE.

If, at the end of the treatment phase with the study treatment, there are pathological laboratory values that were not present at baseline, further clinical or laboratory investigations should be performed until the values return to within reference range or until a plausible explanation (i.e., concomitant disease) is found for the pathologic laboratory values.

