To date, well over 500 patients with hematologic malignancies or solid tumors have been exposed to danvatirsen, and several doses, schedules, and infusion times have been evaluated. Both monotherapy and combination therapy with other anticancer agents have been studied. Consistent with the preclinical data, a bi-phasic pharmacokinetic (PK) profile was noted with an initial fast distribution phase (half-life of 2 to 3 hours) followed by a slower elimination phase. With regard to adverse events (AEs), risks included thrombocytopenia, liver enzyme elevations, anemia, and neutropenia. Overall, danvatirsen demonstrated a tolerable safety profile, and toxicities were well managed with standard guidelines.

The most relevant study of danvatirsen with regard to HNSCC is the SCORES study, which evaluated the addition of danvatirsen to checkpoint blockade. This study included both first-line and second-line patients with R/M HNSCC. The ORR was assessed in 66 evaluable patients treated with danvatirsen at a dose of 3 mg/kg weekly in combination with durvalumab in the first-line setting. In this patient population that was not selected for PD-L1 expression, ORR was 23% (CR 9.1%). The duration of response (DOR) was 42 weeks, indicating a clinically meaningful benefit. Considering that danvatirsen monotherapy in this anti-PD-L1 naïve HNSCC patient population showed no responses, and the historical ORR with durvalumab as monotherapy is also generally regarded as negligible, the combination of danvatirsen and durvalumab appeared to be active and well tolerated. Moreover, additional analyses showed an intriguing relationship between PD-L1 levels and ORR and CRs. In patients with CPS ≥ 1 or CPS ≥ 20 , the combination of danvatirsen and durvalumab led to an ORR of 31% to 37%, and 33% to 43%, respectively (note that the range is due to lack of CPS measures in some patients) and to a CR rate of 11% to 13% in the CPS ≥ 1 subgroup and 19% to 22% in the CPS ≥ 20 subgroup. These outcomes are numerically superior to pembrolizumab historical data in this population.

For the most up-to-date clinical information regarding danvatirsen, refer to the latest version of the Investigator's Brochure.

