### 5.13.1 Adverse Events

Treatment-emergent adverse events (TEAE) are reported according to protocol as any AE that has an onset on or after the first dose of study drug or any pre-existing condition that has worsened on or after the first dose of study drug up to the subject completion of the study.

A treatment-related AE is defined as an AE as being definitely, possibly, or probably, related to the study drug.

All TEAE summaries will include the number and percentage of subjects experiencing each adverse events as well as the total number of events. The following TEAEs will be summarized separately by system organ class and preferred term, as coded by MedDRA dictionary.

- Any TEAE
- Any TEAE (PT only)
- Related to Any Study Treatment
- Related to Danvatirsen
- Serious
- Serious Related to Any Study Drug
- Leading to Discontinuation of All Study Drugs
- Leading to Discontinuation of Danvatirsen only
- Leading to Discontinuation of Pembrolizumab only
- Leading to Dose Delays or Reductions of Any Study Drug
- Leading to Dose Delays or Reductions of Danvatirsen
- Leading to Death
- Leading to Death Related to Any Study Drug
- Toxicity Grade 3 or Higher
- By Maximum Toxicity Grade

An overall TEAE summary table will be provided separately, tabulating the number of subjects and events for any adverse event for the above categories. The following summaries will also be provided.

- Listing of Serious TEAEs
- Listing AEs Leading of Deaths
- TEAE by Preferred Term
- TEAE Related to Any Study Drug by Preferred Term

QMD Ref: Worldwide-TMP-ST-054-1.0_Effective: 12Aug2022	Governing QMD: Worldwide-SOP-ST-026
Confidentiality Statement	

This document is the property of Worldwide Clinical Trials Inc. and may not be duplicated, copied, altered or removed from company without prior approval from Worldwide Quality Assurance or in compliance with Worldwide Standard Operating Procedures.

Worldwide Clinical Trials Controlled Quality Management Document		
 WORLDWIDE CLINICAL TRIALS	Sponsor:	Flamingo Therapeutics
	Protocol Number:	FLM-6774-201
STATISTICAL ANALYSIS PLAN		

All adverse events will be listed. Listings of AEs leading to death will include a flag for on-treatment deaths. An on-treatment death is defined as death occurring from date of first dose of any study drug to 30 days after last dose of Danvatirsen or 90 days after last dose of Pembrolizumab, whichever is later.

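### Protocol 7.9.5 gives two incompatible rules for recording laboratory abnormalities as AEs, so events handled only by a hold, reduction or discontinuation may be missing from the TEAE tables

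*Protocol*

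**What the plan says.** Protocol 7.9.5 opens with a definition: "A clinical laboratory AE is any laboratory value that is deemed clinically significant by the Investigator and is accompanied by one of the following". Three alternatives follow: "Requires a medical intervention"; "Requires a modification or interruption of study treatment"; "Is accompanied by clinical symptoms". Any one is enough, provided the Investigator judges the value clinically significant.

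The paragraph directly after the list gives a different instruction: "Laboratory abnormalities that do not require medical intervention should not be recorded as AEs". It sends such values to the laboratory part of the study report instead. A later paragraph leaves the decision on clinical significance to the Investigator, by reference to the AE criteria and the patient's condition.

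Protocol 1.1.2, summarising earlier experience with danvatirsen, says that "risks included thrombocytopenia, liver enzyme elevations, anemia, and neutropenia". All four are detected by laboratory test. Protocol 9.6 makes AEs the focus of the safety analysis. SAP 5.13.1 plans TEAE tables that include those related to danvatirsen, those of Grade 3 or higher, those leading to discontinuation, and those "Leading to Dose Delays or Reductions of Danvatirsen".

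**The concern.** A laboratory value whose only consequence is a change in dosing is an AE under the list and not an AE under the paragraph after it. A site cannot follow both instructions.

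This matters because several items are collected only through the AE page. Protocol 7.9.4 asks for causality for each AE or SAE, and Protocol 7.9.6 asks for the action taken with each drug for each AE. An abnormality left off the AE page has neither. The SAP grades laboratory values by program for the shift tables (5.13.2) but does not turn them into AEs, so the TEAE tables depend on what sites chose to record.

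Protocol 5.4.1 restricts dose modification to toxicity that is at least possibly related to study treatment. A hold-only event missing from the AE page is therefore, by the protocol's own logic, one that belongs in the treatment-related tables. Tolerability, measured by dose interruptions and reductions, is also part of a secondary endpoint (Protocol Section 2).

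**Working it through.** No figure in the plan bears on this point, so the check is a comparison of texts.

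**Step 1. Apply both instructions to each kind of clinically significant laboratory abnormality.**

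| Consequence of the abnormality | AE by the three-item list? | AE by the exclusion sentence? |
|---|---|---|
| Medical intervention | Yes | Yes |
| Hold, reduction or discontinuation only | Yes | No |
| Symptoms only | Yes | No |
| None of these | No | No |

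The two instructions disagree in two of the four cases, so two of the three qualifying criteria are cancelled.

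**Step 2. Ask whether a dose hold can be read as a medical intervention.** That would remove most of the conflict. The list rules it out, because it gives intervention and treatment modification as separate items.

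**Step 3. Look for a rule that settles the matter elsewhere.** Protocol 5.4.1, 5.4.2, 7.9.1, 7.9.6 and 9.6, and SAP 5.2.6, 5.2.10, 5.13.1 and 5.13.2, contain none. Protocol 7.9.1 allows an abnormal laboratory finding to be an AE. Tables 2 and 3 in Protocol 5.4.2 call the events that trigger danvatirsen holds AEs. Both lean towards recording, but neither says that the exclusion sentence gives way.

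**Step 4. Check that the disputed case can occur.** Table 2 provides for a hold at the first Grade 3 liver-test elevation and discontinuation at Grade 4. Table 3 provides for holds or discontinuation at the higher grades of other events. A liver-test elevation attributed to danvatirsen and managed without steroids fits, as does an untreated thrombocytopenia or neutropenia. For symptoms-only cases the symptom may be entered as an AE in its own right under 7.9.1, so the hold-only case matters more.

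**Step 5. Trace a hold-only event through the planned outputs, assuming the site followed the exclusion sentence.**

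- Missing: the TEAE tables overall, related to danvatirsen, Grade 3 or higher, leading to dose delays or reductions, and leading to discontinuation.
- Still present: CTCAE grade shifts and the listing of laboratory abnormalities (SAP 5.13.2 and Section 11); plots of AST, ALT, hemoglobin, neutrophils and platelets (SAP Section 11); doses delayed, skipped and reduced (SAP 5.11); and discontinuations of each drug with reasons (SAP 5.5).
- Not linked: SAP 5.2.10 classes a dose as delayed or skipped by days since the last dose, without its cause. The shift tables show the grade without the hold or the relatedness.

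**Step 6. Direction.** Danvatirsen holds occur only in the combination arm, so losing them makes the arms look more alike. Pembrolizumab is given in both arms, and Appendix 4 includes laboratory-driven holds that need no treatment. One is Grade 2 hepatitis, where steroids are optional and follow only a lack of improvement; another is a Grade 1 creatinine rise, where a temporary hold may be considered. Hold-only events can therefore also go unrecorded in the control arm.

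**The case against.** The strongest reply is that this is a drafting slip which the surrounding text largely corrects. The closing reference to the AE criteria most naturally means the three-item list, the dose-modification tables call the triggering events AEs, and a SAP table of TEAEs leading to danvatirsen delays presupposes that they are recorded. This is a fair account of probable intent. It does not tell a site which instruction governs, and the exclusion sentence is the more direct of the two.

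Other parts of the reply stand and limit the point:

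- A reader might infer that danvatirsen's main laboratory toxicities drop out of the AE tables as a class. They do not. Transfused anemia and treated neutropenia are AEs under both rules. Under Protocol 5.4.1, inflammatory events without a clear alternative cause are treated as immune related, and Appendix 4 calls for steroids in Grade 3 hepatitis. Such events are also AEs under both rules.
- A reader might infer that every untreated, symptom-free laboratory hold is affected, or that the tables are in fact understated. Only holds at sites that followed the exclusion sentence are affected, and the documents do not show how many did.
- A reader might infer that the loss falls mostly in one arm. Step 6 shows why this is not established.
- A reader might infer that the toxicity itself goes unseen. Grades and missed doses remain in other outputs, and the Safety Review Committee considers laboratory data (Protocol 9.10.1).

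**Conclusion.** The contradiction in Protocol 7.9.5 is explicit and is not resolved in either document. It is a defect in how AEs are recorded, not a loss of safety data. Where the exclusion sentence was followed, events handled only by a dosing change lack the AE entry, causality and action taken, and so fall out of the TEAE tables that describe danvatirsen's tolerability.

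The size cannot be estimated. It depends on which instruction each site applied and on how many laboratory-driven dosing changes involved no treatment. The likely net direction is to understate the difference between arms, because danvatirsen holds are confined to the combination arm. That is not certain, because pembrolizumab laboratory holds can occur in both. The conclusion assumes that the Investigator judged the value clinically significant, as the list requires; this narrows the set of events but does not remove the conflict.

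**What to change.** Replace the exclusion sentence with: *Laboratory abnormalities that meet none of the criteria above should not be recorded as AEs.* This makes the paragraph agree with the list and changes no dosing rule.

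SAP Section 9 says the final analysis will come early because the study is being terminated. The rewording therefore serves mainly patients still on study and sets the rule for queries. The more useful step now is a reconciliation before database lock:

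- In both arms and for both drugs, list every hold, reduction and discontinuation caused by a laboratory value. Protocol 5.4.1 requires reasons for dose modifications to be recorded, so the source should exist. Where the reason is absent, compare dose dates with graded laboratory values.
- Match the list against the AE page and query the unmatched cases, asking for causality and action taken.
- State in the CSR which rule was applied and how many AEs the reconciliation added.

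The cost is one protocol sentence, a memo to sites, and some extra queries and AE entries. Causality for the added events will be assigned in retrospect in an open-label study, which the CSR should say.
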